9. STATISTICAL ANALYSIS.....	17
10. ETHICAL CONSIDERATIONS.....	18
10.1 Regulation statement.....	18
10.2 Recruitment and consent.....	18
10.3 Objection by minors or incapacitated subjects (if applicable).....	18
10.4 Benefits and risks assessment, group relatedness.....	18
10.5 Compensation for injury.....	18
10.6 Incentives (if applicable).....	19
11. ADMINISTRATIVE ASPECTS AND PUBLICATION.....	20
11.1 Handling and storage of data and documents.....	20

11.2	Amendments	20
11.3	Annual progress report	20
11.4	End of study report	21
11.5	Public disclosure and publication policy	21
12.	REFERENCES	22

SUMMARY

Rationale: Invasive fungal infections (IFIs) can be life threatening, especially in prolonged neutropenic patients. The overall mortality in this group has decreased from 60-80% in the past to 30-40% today because of better diagnostics and antifungals. It is essential to diagnose IFIs and start the right treatment as soon as possible to increase survival rates of the patients. Nowadays, HR-CT as imaging technique and galactomannan (GM)-test (Elisa) in blood and fluid (obtained by broncho-alveolar lavage) are together considered the “gold standard” for diagnosing IFIs, but both techniques have their limitations and provide probable diagnosis at best. It is therefore of invaluable importance to have another non-invasive test which can provide a higher sensitivity and specificity for diagnosing these IFIs. ^{18}F -FDG-PET, and even better the combined PET-CT scan (which correlates anatomic with pathophysiologic imaging) might be this important non-invasive imaging technique with better characteristics to early diagnose IFIs.

Objective: The primary objective of this pilot study is to compare FDG-PET-CT with HR-CT alone and to HR-CT and galactomannan test together for early diagnosing IFIs in neutropenic patients.

Study population: Twelve hematologic patients (age > 18 years with neutropenia and prolonged fever after 72 hours of broad-spectrum antibiotics) will be included in this study. Six of 12 patients will have positive signs (one nodule or more noduli) on the HR-CT for IFI and a positive galactomannan-test, therefore having a probable IFI per definition. Furthermore, six out of 12 patients will have positive signs on HR-CT scan without a positive GM test, therefore having a possible IFI.

Study design: All twelve patients will undergo, within 48 hours of the HR-CT, an FDG-PET-CT scan (low dose CT) on the mCT (Siemens) camera at the Department of Nuclear Medicine and Molecular Imaging. The FDG-PET-CT will be evaluated qualitatively and quantitatively by calculation of the maximal Standardized Uptake Value (SUV_{max}). These quantitative parameters will be correlated with the results of the galactomannan-tests. Treatment schedule will be similar as normal treatment procedures, i.e. treatment regimen will not depend on the results of the FDG-PET-CT. We hope to find that FDG-PET-CT is able to localize IFI with more accuracy and give us pathognomic signs in this group of patients for having an IFI. This pilot study can form the basis for larger patient studies to see if FDG-PET-CT is able to detect IFI with greater sensitivity and specificity and eventually replace the invasive galactomannan-test by broncho-alveolar lavage.

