4.2 Inclusion criteria

Adult patients (age > 18 years) with a hematologic disease who probably or possibly have an IFI. That means:

- Prolonged (or expected prolonged) neutropenia (leukocyte count < $1,0 \times 10^9$ or granulocyte count < $0,5 \times 10^9$, or leukocyte count < $1,5 \times 10^9$ or granulocyte count < $1,0 \times 10^9$ and decreasing due to chemotherapy), and
- Axillary temperature $\geq 38,5^\circ\text{C}$, not reacting on treatment with wide-spectrum antibacterial drugs for 72 hours, and
- A positive HR-CT scan, suspect for an IFI and
 - A positive galactomannan-test in serum or fluid acquired by BAL, or positive in both materials (N=6)
 - A negative galactomannan-test GM in both serum and BAL fluid (N=6)

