4.3 Exclusion criteria

- Patients with age < 18 years
- Female patients who are pregnant
- Patients with claustrophobia or other reasons that make the scanning impossible, such as unable to lie still, need of oxygen, and so on.
- Patients who are hemodynamically instable
- (Pre)terminal patients for which the investigation is too burdensome
- Patients who may clinically not be able to undergo the study
- Patients without prolonged or expected prolonged immunocompromised condition (less than 14 days)
- Patients without positive signs of IFI on HR-CT

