7.3 Study procedures

When the (conventional) diagnostic tools are performed and a patient probably or possibly has an invasive fungal infection, FDG-PET-CT (low dose CT) scan will be planned as soon as possible, but within 48 hours of the HR-CT scan on the mCT camera (Siemens).

When the (conventional) diagnostic tools are suspicious for an IFI antifungal treatment will be started, independent of the FDG-PET-CT results. Treatment will be continued conform normal treatment procedures, i.e. treatment regime will not depend on the results of the FDG-PET-CT.

Patient recruitment:

Informed consent will be obtained by [name] or [name] from the Department of Internal Medicine, Division of Hematology. When the patient decides to participate he/she will be asked to sign the informed consent form. The normal diagnostic and therapy protocols will not be changed; other imaging studies will not be delayed. Patients can contact an independent doctor (Dr. [name]) in case they feel the need to receive information from a doctor who is not involved in the study.

Preparation and labelling of [¹⁸F]-FDG:

¹⁸F-FDG will be prepared according to the standard protocol at the department of Nuclear Medicine and Molecular Imaging as is described in the IMPD.

[¹⁸F]-FDG-PET-CT protocol:

A routine whole body PET (that means from head till halfway the upper legs) will be performed 60 minutes after the intravenous injection of 3-5 MBq per kilogram [¹⁸F]-FDG conform normal administrated activity in patients. A low dose CT will be

performed simultaneously for attenuation correction and for anatomic correlation with the PET images. The total scanning time will be around 25 minutes.

Evaluation of the FDG-PET-CT scan:

The FDG-PET-CT will be evaluated qualitatively and quantitatively by an experienced nuclear medicine physician, with special attention to finding lesions outside the thorax, the extension of the lesions found compared to the HR-CT lesions and to the intensity of the uptake of FDG by calculating the SUVmax. These quantitative results will be compared to the results of the galactomannan-tests.

Radiation dose considerations:

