9. STATISTICAL ANALYSIS

Statistical analysis is not necessary in this pilot study. The lesions found on the FDG-PET-CT will be described in the report and compared to other diagnostic techniques. The FDG-PET-CT scan will be evaluated qualitatively (by visual evaluation of the uptake) and quantitatively (by calculating the SUVmax). The calculated SUVmax will be compared to the results of the galactomannan-tests. The aim of this study is to see if FDG-PET-CT is able to localize the IFI and if pathognomic signs for IFIs can be found.

We expect positive signs on the FDG-PET scan in all patients with probable fungal infections. Of the six patients with possible infections we expect at least 2 or 3 to have positive signs on FDG-PET scan. If we can find additional information (positive lymph nodes, lesions in other part of the body) we can not predict.

When there is added value of the FDG-PET-CT we will arrange a larger patient study for which statistical analysis is necessary. Power calculation is not applicable in this study because the aim of this study is to get data to plan a larger clinical study with the appropriate power calculation. These data will serve to calculate the power analysis for a subsequent clinical study.

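### A positive HR-CT is an entry condition and PET-CT follows it, so the primary comparison with HR-CT alone cannot show added patient detection or earlier diagnosis, and no PET sign can be shown to be pathognomonic.

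*Protocol*

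**What the plan says.** The Summary gives the primary objective as to "compare FDG-PET-CT with HR-CT alone and to HR-CT and galactomannan test together for early diagnosing IFIs in neutropenic patients". The lead sentence of Section 2 repeats the aim as added value for early diagnosis, then lists specific questions on lesion characteristics, extension, lymph nodes, additional or smaller lesions, sites outside the thorax, and uptake in relation to GM.

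Eligibility and test order are fixed as follows:

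- Section 4.2 requires "A positive HR-CT scan, suspect for an IFI and" either a positive or a negative GM result, six patients of each.
- Section 4.3 excludes "Patients without positive signs of IFI on HR-CT".
- Section 7.3 starts the PET step "When the (conventional) diagnostic tools are performed and a patient probably or possibly has an invasive fungal infection", and the "scan will be planned as soon as possible, but within 48 hours of the HR-CT scan".

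Section 3 classes all 12 patients as probable or possible IFI. The Summary hopes that "FDG-PET-CT is able to localize IFI with more accuracy and give us pathognomic signs in this group of patients" for having an IFI. Section 9 makes it part of the study's aim to see "if pathognomic signs for IFIs can be found".

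**The concern.** The comparator is also the entry ticket. When one of two tests selects the sample, the paired comparison at patient level is partly settled before the first scan. Here the selecting test is the one that PET is to be compared with.

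Pathognomonic status raises a second difficulty. A sign is pathognomonic if it does not occur without the disease, so the claim needs patients known not to have IFI. None are planned. Section 1 says that biopsy, the only proof named, is often not possible.

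No test is planned, so no error rate is at stake. What is at stake is the conclusion. Section 9 makes added value the trigger for a larger study and says that these data will feed its power calculation. Section 10.4 hopes that PET-CT becomes the imaging method of choice. If added value is read as in the Summary objective, the pilot cannot supply the evidence. It also cannot supply one key planning figure for a PET versus HR-CT study: how often PET is positive when HR-CT is negative.

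**Working it through.** **Inputs.** N = 12, made up of 6 probable (GM-positive) and 6 possible (GM-negative), from Sections 3 and 4.2; 6 + 6 = 12 agrees. Expected PET positivity from Section 9: all 6 probable, and at least 2 or 3 of the 6 possible. The number of patients truly without IFI is not given; Section 4.4 says only that most have IFI. No alpha, power or effect size is stated, so there is no sample size calculation to reproduce.

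**1. PET against HR-CT alone, patient level.** Let k be the number of PET-positive patients.

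| | HR-CT positive | HR-CT negative |
|---|---|---|
| PET positive | k | 0 by design |
| PET negative | 12 − k | 0 by design |

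The difference in positivity, PET minus HR-CT, is (k − 12)/12, which is at most 0 for every k from 0 to 12.

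- k = 6 + 2 = 8: (8 − 12)/12 = −33 percentage points, 4 discordant patients.
- k = 6 + 3 = 9: (9 − 12)/12 = −25 points, 3 discordant patients.
- k = 12: 0, a tie.

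Since Section 9 says at least, 8 to 9 is a floor. All discordant patients are PET-negative and HR-CT-positive, whatever the true state of disease.

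**2. Timing.** PET is planned after the conventional tests have been done. No patient can yield a PET diagnosis before the HR-CT finding.

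**3. What the PET-negative patients mean.** Suppose m of the 12 do not have IFI (an assumption, taken from 0 to 4), and t of these m are PET-negative. Within the sample HR-CT has sensitivity 100%, and for m of 1 or more its specificity is 0/m = 0%, both by selection. PET sensitivity is [(12 − m) − (12 − k − t)]/(12 − m), and PET specificity is t/m. With the same observed result, k = 8:

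| Assumed m | t | PET sensitivity | PET specificity |
|---|---|---|---|
| 0 | – | 8/12 = 67% | not estimable |
| 4 | 4 | 8/8 = 100% | 4/4 = 100% |
| 4 | 0 | 4/8 = 50% | 0/4 = 0% |

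One observed count fits a PET scan that is perfect and one that is poor. Only a reference diagnosis independent of HR-CT and GM could separate these cases, and the protocol fixes none.

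**4. PET against HR-CT plus GM.** The combined comparator is positive in 6/12 by design. At the Section 9 floor PET is positive in 8 to 9 of 12: (8 − 6)/12 = +17 points to (9 − 6)/12 = +25 points. This contrast can go either way on positivity. Whether an extra PET-positive patient is a true positive stays unknown, for the reason in step 3.

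**The case against.** The strongest defence is that Section 2 already spells out what added value means, and its questions are mostly about lesions: characteristics, extension, lymph nodes, smaller or additional lesions, and sites outside the thorax. None of them needs an HR-CT-negative patient, and a whole-body PET can show sites that a thoracic HR-CT cannot. The language is also cautious: the Summary speaks of hope, Section 9 of seeing whether. Greater sensitivity and specificity are left to larger studies, and treatment does not depend on the scan. All of this stands, and it lowers the severity. It does not remove the mismatch, because the headline objective and the Section 9 aim go beyond those questions.

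A second defence is that early may mean an early stage of disease, since Section 1 uses the term that way for the air crescent sign. That reading is possible. It does not rescue the aim, because every patient enters only once disease is suspected on HR-CT, so PET at a stage before HR-CT signs is never observed.

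A reader might go further and infer that PET can only tie with HR-CT or lose, or that a perfect PET would score 12/12. The documents do not support this. Section 4.4 says only that most patients have IFI, and Section 1 describes HR-CT as often inconclusive and its signs as non-specific. A perfect PET would be negative in an HR-CT false positive, and would then be the better test. The trouble is that such patients cannot be identified here.

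**Conclusion.** The point holds at patient level against HR-CT alone. Two of the four cells of the paired table are empty by design, so a gain in detection or timing is impossible to observe. A specificity gain is possible in truth but cannot be shown, and pathognomonic status cannot be shown, for want of a non-IFI group and an independent reference standard. The first conclusion rests only on Sections 4.2, 4.3 and 7.3 as written; the second on the absence of such a standard from the protocol.

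It does not follow that the pilot is uninformative, as a reader might infer. The contrast with HR-CT plus GM, on positivity, and the Section 2 questions on lesions and extrathoracic sites can be answered descriptively. With a descriptive pilot of 12 patients and accuracy deferred to a later study, this should be fixed but is not critical.

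**What to change.** Align the Summary objective, the lead sentence of Section 2 and the aim in Section 9 with the questions already listed in Section 2. Suggested wording: *Among HR-CT-positive neutropenic patients, to describe (a) FDG uptake at HR-CT lesions and the extension of these lesions; (b) lesions seen on only one modality, including outside the thorax; and (c) PET findings and SUVmax by GM status.*

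- Remove early diagnosis and pathognomonic signs as aims. Replace the latter with *candidate uptake patterns for testing in a later study that includes patients without IFI*.
- State that no conclusion will be drawn on a gain over HR-CT in sensitivity, specificity or timing.
- State that added value, as the trigger for the larger study, is judged on the lesion-level and GM-related findings.

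Item (c) should stay descriptive. Section 1 notes that GM misses fungi other than Aspergillus. With six patients per group, even 6/6 against 2/6 or 3/6 gives a two-sided Fisher p of 2 × 15/495 = 0.06 or 2 × 20/220 = 0.18.

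The cost is a wording amendment and a less ambitious claim; patients and procedures are unchanged. Keeping the comparison as stated would instead require HR-CT-negative febrile neutropenic patients and a reference diagnosis independent of HR-CT, GM and PET, which belongs in the larger study.

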1. INTRODUCTION AND RATIONALE

Invasive fungal infection (IFI) can be life threatening, especially in neutropenic patients. One of the most notorious pathogens causing these infections is a mold called *Aspergillus*. Diagnosing IFI in neutropenic patients is difficult. A lung biopsy as golden standard for proven invasive aspergillosis is often not possible due to thrombocytopenia and due to a difficult procedure to reach non-peripheral localized lung lesions. Furthermore, there is a chance of pneumothorax after this CT-guided biopsy has been performed. The benefit of a broncho-alveolar lavage (BAL) is also questionable when peripheral localized lung lesions are involved because the BAL fluid will not reach these lesions. On the other hand it may be helpful to exclude other causes of neutropenic fever, like PCP or viral pathogens. Nowadays High Resolution CT-scan (HR-CT) of the thorax and a galactomannan-test (galactomannan is a component of the cell wall of the aspergillus) in serum and fluid acquired by BAL are the next best ("silver") standard procedures for diagnosing IFIs.

However, galactomannan (GM) has a low sensitivity for fungal infections in general; it is only suitable for infections caused by *Aspergillus*, but other fungi, such as *mucor*, are not detected with this test. The sensitivity and specificity of GM detection in BAL fluid was 88 and 87%, respectively. However, the sensitivity of serum GM was only 42%. [1] Pathognomonic signs on the HR-CT scan are the *halo sign* (a zone of low density surrounding the real lesions), the *air crescent sign* (lung cavities filled with air and a round radio opaque mass, which can only be seen in advanced and prolonged IFIs after recovering of neutrophils in the blood and therefore not in an early stage of IFI), and nodular lesions. In the clinical setting, HR-CT is often inconclusive because the afore mentioned signs can be aspecific, e.g. the halo-sign can also appear in other infectious and non-infectious diseases, such as neoplastic and inflammatory conditions, or even disappear within a few days. [2] Another disadvantage of the HR-CT of the thorax is that non-infectious pathology and lesions outside the lungs cannot be visualized.

Treatment of IFIs remains, even when recognized early, problematic because the response of a patient on antifungal treatment depends on the depth and the duration of this immunosuppressed (mostly granulocytopenic) condition. Therefore, it is essential to diagnose IFIs and start the right treatment as soon as possible to increase survival rates of the patients. It is therefore of invaluable importance to have an imaging method for diagnosing these IFIs that has a higher sensitivity and specificity than the HR-CT with and without the galactomannan-test. Therefore, we want to study the added value of FDG-PET-CT compared to the HR-CT with and without a positive galactomannan-test.

¹⁸F-FDG-PET, and even better the combined PET-CT scan (which correlates anatomic with pathophysiologic imaging), will maybe be this important non-invasive imaging technique to early diagnose IFIs.

FDG-PET is used already for many years in daily practice in many infectious diseases. This technique is also used incidentally in various fungal infections, such as aspergillosis, candidiasis, histoplasmosis, coccidioidomycosis, cryptococcosis and *Pneumocystis jiroveci*. [3-9] However, systematical use of FDG-PET in patients suspected of IFIs is virtually absent.

Sometimes these infections were found by coincidence in patients that were scanned for other reasons such as (recurrent) malignancy.

The largest study was published by Chamilos et al. who reported their own experiences in 13 patients with the results of nine patients in literature. Most patients had an underlying malignancy (73%), primarily of haematological origin (55%) and 7 were allogeneic haematopoietic stem cell transplants recipients. Importantly to notice, the vast majority of these immunocompromised patients (82%) were non-neutropenic at the time of diagnosis of IFI. They found that FDG-PET frequently found occult lesions not found with other imaging techniques (3 out of 16 patients with available follow FDG-PET imaging studies), and that the results helped to determine treatment length in 8 of these 16 patients. Overall, FDG-PET was deemed to be helpful in 10 out of the 16 (60%) eligible patients. [10] However, it remains unclear whether these results also apply for neutropenic patients.

For the combined PET-CT almost no studies were found in literature for the indication 'fungal infections in neutropenic patients'. Three reports of in total five patients showed that FDG-PET-CT is effective in diagnosing IFIs. [11-13]

In this study we will include patients who have a possible or probable IFI, which means positive signs on the HR-CT for IFI and without or with a positive galactomannan-test in blood and/or BAL. To get final proof of IFI a biopsy would be necessary, however as explained before, this is often not possible due to the thrombocytopenic state of the patients. We hope to find pathognomic signs on the FDG-PET-CT that probably can replace the now needed invasive galactomannan-test by broncho-alveolar lavage, which is a considerable burden for the patient and not performable when the patient is clearly dyspnoic.

2. OBJECTIVES

Primary Objective:

To evaluate if FDG-PET-CT has added value compared to HR-CT and galactomannan-test, nowadays the silver (or surrogate gold) standard diagnostic techniques for early diagnosing IFIs in neutropenic patients. To evaluate this added value we have the following questions:

- Has FDG-PET-CT additional value as imaging modality compared to the HR-CT thorax? Are their specific imaging characteristics found on FDG-PET-CT in relation to the 3 different described lesions found by HR-CT? Can FDG-PET-CT also provide information about the extension of the known lesions, i.e. is the halo sign on HR-CT involved in the infectious process or is it a sign of decreased perfusion due to infarction?
- Can FDG-PET-CT detect enlarged and/or positive lymph nodes and what is the meaning of these lymph nodes in relation to prognosis or GM detection?
- Is FDG-PET-CT able to find additional infectious lesions that are not visible on HR-CT of the thorax? Can FDG-PET-CT detect smaller lesions than HR-CT by its metabolic positivity and is there a relation between the total amount of metabolic positivity of lesions (mean SUV times area of positivity) and galactomannan positivity, which is a parameter of activity and/or invasiveness of aspergillosis?
- Is FDG-PET-CT able to find additional infectious lesions that are not visible on HR-CT of the thorax because they are found outside the thorax? Sometimes IFI are found in the sinussen or gut or brain or combinations of these localisations.

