4.4 Sample size calculation

This study is a pilot study in twelve hematologic patients who have a probable or possible IFI. Because most of these patients will actually have an IFI, we think these are enough patients to study the added value of FDG-PET-CT in this group of patients to conclude if larger patient studies are wanted.

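### The total metabolic positivity in section 2 is defined as mean SUV times area; a total needs volume, and sections 7.3 and 9 do not name the measure at all

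*Protocol*

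**What the plan says.** Under the primary objective (section 2), one question is whether GM positivity is related to the "total amount of metabolic positivity of lesions (mean SUV times area of positivity"). The wording names a total, and the bracket gives its formula. The same sentence describes the other variable as "galactomannan positivity, which is a parameter of activity and/or invasiveness of aspergillosis".

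The protocol does not say how the area is taken (one slice, the largest cross-section, or a sum over slices) or how several lesions are combined. Nothing elsewhere replaces area by volume.

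The number of lesions will differ between patients, because the Summary admits those with "positive signs (one nodule or more noduli) on the HR-CT". The scan covers most of the body (section 7.3): "A routine whole body PET (that means from head till halfway the upper legs) will be performed".

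The only uptake measure in the methods and analysis sections is SUVmax. Section 7.3 speaks of the "intensity of the uptake of FDG by calculating the SUVmax", and section 9 states: "The calculated SUVmax will be compared to the results of the galactomannan-tests". Section 9 also states: "Statistical analysis is not necessary in this pilot study".

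**The concern.** Mean concentration times volume gives a total amount; mean concentration times area gives an amount per unit of thickness. Cross-sectional area grows with the square of the diameter and volume with the cube. Adding areas over lesions therefore gives small nodules too much weight against large ones and ignores extent along the body axis.

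Lesion number and size will probably vary between these patients, and section 2 itself hopes to find smaller and extrathoracic lesions. This is the setting in which the two indices part. The quantity set against GM status would then not be the total burden that the question names. Section 9 wants the pilot's data to inform the power calculation of a later study, so a mis-specified index could be carried forward.

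**Working it through.** The protocol gives no figure for this index, so there is none to reproduce. It also gives no lesion sizes, counts or SUVs; those used below are assumptions.

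**Inputs from the protocol.** The index formula (section 2); one or more nodules per patient (Summary); 12 patients, 6 GM-positive and 6 GM-negative (section 4.2), hence 12 × 11 / 2 = 66 patient pairs.

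**Geometry.** For a sphere of diameter d, cross-sectional area = πd²/4 and volume = πd³/6.

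**Step 1: does the index behave as a total?** Split one sphere of diameter D into k equal spheres of the same total volume. Each has diameter D/k^(1/3), so the summed area is k × πD²/(4k^(2/3)) = k^(1/3) × πD²/4. At equal SUV the total uptake is unchanged, yet the index is multiplied by k^(1/3):

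| k | Factor |
|---|---|
| 2 | 1.26 |
| 4 | 1.59 |
| 8 | 2.00 |
| 10 | 2.15 |

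**Step 2: can patients change order?** At equal mean SUV:

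| Patient | Summed area | Summed volume |
|---|---|---|
| One 40 mm nodule | 12.6 cm² | 33.5 mL |
| Five 20 mm nodules | 15.7 cm² | 20.9 mL |
| Ratio, second to first | 5 × 20²/40² = 1.25 | 5 × 20³/40³ = 0.63 |

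By area the second patient has 25% more; by volume the first has 60% more (33.5/20.9 = 1.60). Eight 15 mm nodules against one 40 mm nodule give 8 × 15²/40² = 1.13 by area and 8 × 15³/40³ = 0.42 by volume, again a reversal.

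**Step 3: how often in plausible mixes?** Two sets of simulations of 12 patients, 4,000 runs per setting:

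- 1 + Poisson(2) lesions per patient, median diameter 20 mm with log-SD 0.3-0.7, and lesion height varying with log-SD 0-0.5. On average 2.6 to 8.9 of the 66 pairs changed order (2.6/66 = 4%, 8.9/66 = 13%). The Spearman correlation between the two indices was 0.86-0.98.
- Up to 3 or up to 10 spherical lesions, diameter 0.8-4 cm, SUV 2-8. About 5% of pairs changed order, and the Spearman correlation was about 0.97.

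**Step 4: sensitivity to contouring.** A 10% error in diameter gives 1.1² = 1.21 (21%) in area and 1.1³ = 1.33 (33%) in volume.

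**The case against.** **Area may not mean one slice.** Section 2 does not say so. If area is summed over slices of constant thickness, the index is proportional to volume and no ranking changes: for a 4 cm sphere in 2 mm slices, summed area times thickness is 33.55 cm³ against a true 33.51 cm³. This reading is possible but not stated, and one cross-section per lesion is the plainer one. If slice-summing was intended, the corrected wording says so at no loss.

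**The index is not in the planned evaluation.** Sections 3, 7.3 and 9 name only SUVmax. This stands: changing one word in section 2 would alter nothing that the methods say will be computed. It widens the fix but does not make the formula right.

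**Nothing depends on it.** Section 4.4 reads: "This study is a pilot study in twelve hematologic patients who have a probable or possible IFI". No test, sample size or treatment decision uses the index. This also stands, and it limits the weight of the point.

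**A stronger reading.** A reader might infer that patients will in general be ranked wrongly and that a correlation with GM will be weakened. One can simulate this: a correlation of about 0.62 with the volume index becomes 0.56-0.61 with the area index. The documents do not support using that as the size of the harm. It treats GM as continuous and assumes that GM follows volume. The protocol asks about GM positivity, which section 4.2 makes positive or negative, and nowhere says that GM tracks lesion volume. Even on its own terms the loss of 0.01-0.06 is lost in the noise: the 95% Fisher interval for r = 0.62 with 12 patients runs from about 0.07 to 0.88.

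**Conclusion.** The point holds as a minor one. On its plain reading, the section 2 formula does not give the total that it is named for, and it over-weights patients with many small lesions by k^(1/3) at equal SUV and equal total volume. Reversals of order are real but need contrasting lesion patterns; under the assumed mixes about 4-13% of pairs are affected and the two indices otherwise agree closely. The effect on a descriptive 6 v 6 comparison by GM status is likely small.

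This rests on reading area as one cross-section per lesion, on roughly spherical lesions, and on assumed sizes and counts. It does not show that the pilot's conclusions would be wrong. It is still worth correcting, because the right quantity can be had from the scan already planned.

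**What to change.** In section 2, replace the bracket by: mean SUV times volume of positivity, summed over the patient's lesions. In sections 7.3 and 9, name the same measure beside SUVmax, so that it is computed and compared descriptively between GM-positive and GM-negative patients.

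No extra scan or reader is needed. Mean SUV already requires a lesion contour, and on three-dimensional PET data that contour gives the volume. The cost is slightly more image-analysis work. Because volume is more sensitive than area to contouring error, the same contour rule should be used for all patients; its detail can go in an analysis plan.
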